**Table 4-1 PFS or DOR (responders only) outcome and censoring definition**

Situation	Date of event or censoring	Outcome
No adequate post-baseline disease status assessment unless death occurs prior to first post-baseline assessment	Date of first study treatment	Censored
Death due to any reason before PD	Date of death	Event
PD	Date of PD	Event
No PD or death due to any reason on or before a. database cut, b. withdrawal of informed consent, c. lost to follow-up, d. start of new antineoplastic treatment, whichever occurs first	Date of last adequate disease assessment on or prior to the earliest occurrence of the events (a. – d.) listed in the left column	Censored
No PD or death due to any reason	Date of last adequate disease assessment prior to the gap	Censored

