### 1.4. STUDY PLAN

For each patient that signs the informed consent, the study consists of:

- Screening/baseline visit: occurs within 21 days prior to receiving the 1st dose of study treatment
- Treatment period: There is no maximum treatment duration. Treatment cycles of arm A and B last 42 days and arm C last 28 days. Patients may continue to receive study drugs until the patient has confirmed PD, withdraws consent, is lost to follow-up, experiences intolerable toxicity which precludes further treatment, or treatment is discontinued at the discretion of the patient, Investigator, or Karyopharm. Patients who have objective disease progression but have evidence of overall clinical benefit may, at the request of the treating physician, continue treatment with study drugs after discussion with the Medical Monitor.
- Follow-up period: durability of response and survival phone call will be made to patient every 3 months up to one year after last dose of study treatment.

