## **2.3. STUDY TREATMENT DOSING DATE**

Study treatment dosing date is the date on which a patient actually received study treatment (partial or complete), as recorded on the study drug exposure eCRF.

The date of first study treatment is defined as the earliest date of non-zero dose of study treatment.

The date of last study treatment is defined as the latest date of non-zero dose of study treatment.

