### **3. PATIENT INFORMATION**

#### **3.1. DISPOSITION OF PATIENTS AND ANALYSIS POPULATIONS**

Patient disposition will be summarized in each of the following categories:

- Patients who were randomized
- Patients who were randomized and received at least one dose of the study treatment (partial or complete)
- End of treatment:
  - Patients who discontinued treatment and primary reason for discontinuation
- Survival follow-up status
  - Patients in survival follow-up
  - Patients who died during survival follow-up
- End of study
  - Patients who discontinued from study and primary reason for study discontinuation

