##### **3.1.1. Intent-to-Treat (ITT) Population**

Intent-to-Treat Population (ITT): All patients randomized to study treatment. Patients will be analyzed in the treatment arm to which they were randomized.

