## 4. EFFICACY

Response assessment will be determined per RECIST 1.1 for all arms at the time points specified by the investigator. All efficacy analyses will be performed on the ITT Population.

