#### 4.1.3. Progression-free Survival (PFS)

PFS is defined as the time from the randomization date until the date of first PD determined by PI per RECIST 1.1, or death due to any cause, whichever occurs first. The outcome and censoring definitions are provided in Table 4-1. The number and percentage of censored patients will be reported. The 25th, 50th (median), and 75th percentiles for PFS and associated 95% CIs will be estimated based on the KM method.

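### Table 4-1 censors PFS at first dose although PFS runs from randomisation in the ITT population, so a living randomised patient who is never dosed and never scanned has no PFS time

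*SAP*

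**What the plan says.** - **Time origin.** SAP section 4.1.3: "PFS is defined as the time from the randomization date until the date of first PD determined by PI per RECIST 1.1", or death if that comes first.
- **Population.** SAP section 4: "All efficacy analyses will be performed on the ITT Population". Section 3.1.1 defines that population as "All patients randomized to study treatment", with no requirement to have been dosed.
- **Censoring rule.** The first row of Table 4-1 covers patients who have no adequate assessment after baseline and did not die before one. Its censoring date is "Date of first study treatment".
- **Meaning of that date.** SAP section 2.3: "The date of first study treatment is defined as the earliest date of non-zero dose of study treatment".
- **Undosed patients are foreseen.** Section 3.1 tabulates all randomised patients and, as a separate line, those who were randomised and received at least one dose.
- **Required output.** Section 4.1.3: "The number and percentage of censored patients will be reported". Section 4.2 asks for the same for all time-to-event endpoints.

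**The concern.** The origin of PFS and its population are tied to randomisation, but the first-row censoring date is tied to dosing. For a randomised patient who is never dosed, has no post-baseline scan and is not known to have died, the table points to a date that does not exist. The analysis would have to include this patient but could not compute a time.

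Someone programming the endpoint would then have to choose between dropping the patient, falling back on the baseline scan, or using randomisation. In an open-label trial with 26 patients per arm, early withdrawals by arm matter to a reader judging the comparison, and these are the patients who could disappear from the PFS table.

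There is also a lesser inconsistency. A first-row patient who was dosed does get a date, but is credited with the interval from randomisation to first dose as progression-free time with no assessment behind it.

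**Working it through.** **1. Does any rule give the patient a date?** Take a randomised patient with no dose, no post-baseline scan and no death.

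| Table 4-1 row | What it needs | Available? |
|---|---|---|
| 1, no adequate post-baseline assessment | a first non-zero dose (section 2.3) | No |
| 2, death before progression | a date of death | No |
| 3, progression | a date of progression | No |
| 4 and 5, no progression or death | a last adequate disease assessment | None after baseline |

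Elsewhere, section 2.2.1 deals with missing dosing dates only for treatment duration, which it leaves missing. The sponsor's rule book is cited only for adverse event, medication and birth dates (sections 2.2.2 and 2.2.3). OS has its own censoring rule that does not depend on dosing (section 4.1.5), so the same patient can contribute to OS and have no PFS value.

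**2. Who is not affected.** Undosed patients who die before a first assessment fall under row 2, and undosed patients with scans fall under the later rows. Row 1 cannot arise for DOR, because a responder has a post-baseline assessment by definition.

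**3. Hazard ratio and median.** A patient censored at randomisation leaves before the first event, so is in no risk set and adds nothing to the Cox partial likelihood or to any Kaplan-Meier step. Dropping the patient therefore gives the same result. An illustrative data set (26 per arm, assumed exponential times) agrees:

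| Affected control patients | HR, censored at day 1 | HR, dropped |
|---|---|---|
| 1 | 0.7065 | 0.7065 |
| 2 | 0.7339 | 0.7339 |
| 3 | 0.561 | 0.561 |

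The control median was also the same under both treatments in each case.

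**4. Reported censoring.** Arm size is 26 (section 1.3; 3 × 26 = 78 agrees with the stated total). Let k be the affected patients in an arm and c the other censored patients. Neither is in the SAP, so assume k = 1 to 3 and c = 3 to 8.

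- If affected patients are dropped: c / (26 − k)
- If they are censored at randomisation: (c + k) / 26

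| c | k | Dropped | Censored at randomisation | Gap (points) |
|---|---|---|---|---|
| 8 | 1 | 8/25 = 32.0% | 9/26 = 34.6% | 2.6 |
| 5 | 1 | 5/25 = 20.0% | 6/26 = 23.1% | 3.1 |
| 5 | 2 | 5/24 = 20.8% | 7/26 = 26.9% | 6.1 |
| 5 | 3 | 5/23 = 21.7% | 8/26 = 30.8% | 9.0 |
| 3 | 3 | 3/23 = 13.0% | 6/26 = 23.1% | 10.0 |

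The gap equals k(26 − k − c) / [26(26 − k)]. Over the assumed ranges it is smallest at c = 8, k = 1 and largest at c = 3, k = 3.

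**5. Dosed first-row patients.** The SAP gives no randomisation-to-dose interval. Section 1.4 says that the screening visit "occurs within 21 days prior to receiving the" first dose, so if randomisation follows that visit the credited lag is 0 to 21 days. Suppose one event falls inside the lag while one such patient is still counted at risk. The Kaplan-Meier step is then 1/26 = 3.8% instead of 1/25 = 4.0%, a difference of 0.15 points.

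**The case against.** The strongest objection concerns consequence. No inferential result changes, and the equality of the hazard ratios is guaranteed by how risk sets work, so simulation adds nothing to it. That is right: what is at stake is the completeness of the primary-endpoint table, not the treatment estimate.

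Second, the SAP does not prescribe dropping these patients. Its ITT rule forbids it, so strictly the plan leaves their handling unresolved. This is fair, but an ITT rule that requires a value and a table that cannot supply one is the contradiction at issue.

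Third, section 2.1 bases percentage denominators on the analysis population. The denominator would then stay at 26 and the gap would be k/26, whatever c is: 3.8 points for one patient, 11.5 for three. This is a reasonable reading, and it makes the understatement larger than the range shown above.

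Fourth, row 4 does not say that its last adequate assessment must be after baseline, so the baseline scan might be used. That is a weak fallback. Row 1 is the specific rule for this patient, and a baseline scan may precede randomisation, giving a zero or negative time.

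Finally, the number of affected patients is assumed and could be zero, and the lag for dosed patients is negligible in practice. Both points stand.

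**Conclusion.** The concern holds. The first-row censoring date conflicts with the PFS origin and with the ITT population, and it leaves an identifiable type of randomised patient with no primary-endpoint time. This follows from the SAP's text and needs no assumption.

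The size does rest on assumptions. With 1 to 3 such patients in an arm of 26 and 3 to 8 others censored, reported censoring is too low by 2.6 to 10.0 points if they are dropped. It is too low by 3.8 to 11.5 points if they go uncounted against a denominator of 26. The hazard ratio and median are the same as with censoring at randomisation, and OS and DOR are unaffected. The rule should be corrected because it is wrong as written for the primary endpoint, although it does not threaten the trial's conclusion.

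**What to change.** In the first row of Table 4-1, for PFS, replace the date of first study treatment with the date of randomisation. Every randomised patient then has a defined time: 0 days for the affected patients, or 1 day if the derivation adds one. The PFS N then equals the ITT N, and dosed first-row patients are no longer credited with unassessed time. The cost is one table cell in the SAP and the matching line of the PFS derivation. Trial conduct and data collection do not change.

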## **4.2. STATISTICAL METHODS FOR EFFICACY ENDPOINTS**

Binary endpoints of ORR and DCR will be calculated by point estimate with a 95% confidence interval (CI) using the exact method.

The analysis of time-to-event endpoints (PFS, OS, DOR) will be based on Kaplan-Meier method for estimation of summary statistics and will include the median event times and associated 95% CIs, as well as the number and percentage of censored patients. In addition, Cox proportional hazards regression models will be used to estimate a HR for the risk of progression in the selinexor only or selinexor and pembrolizumab arm versus the SOC control arm, and the selinexor and pembrolizumab arm versus selinexor only arm comparisons.

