## 1. OVERVIEW AND INVESTIGATIONAL PLAN

### 1.1. OVERALL DESIGN

This is a phase 2, open-label, multicenter study that will evaluate the efficacy and safety of selinexor and pembrolizumab in patients with advanced or metastatic CRC. The study schema is depicted in [Error! Reference source not found.](#).

**Figure 1** Study Schema

SOC = Standard of care, PD = progressive disease; MSI-H = microsatellite instability high; dMMR = deficient mismatch repair; QW = once weekly; BID=twice daily; CRC=colorectal cancer

Approximately 78 patients with advanced or metastatic CRC will be enrolled, and randomized to Arm A, B or C based on the following stratification factor:

CCI

All eligible patients in Arm A will be treated with selinexor 80 mg QW orally as a monotherapy on Day 1 of each week of a 42-day cycle. Arm B patients will be treated with selinexor at the same dose as Arm A in combination with pembrolizumab 400 mg IV once every 6 weeks. Arm C patients will be administered the standard of care treatment trifluridine and tipiracil 35 mg/m^2/dose orally BID (max 80 mg / dose) on Days 1 through 5 and Days 8 through 12 of each 28-day cycle. Trifluridine and tipiracil should be taken with food.

Primary efficacy will be assessed by PFS, as assessed by the investigator per [RECIST1.1](#) for selinexor plus pembrolizumab and for SOC assessed from randomization until disease progression or death from any cause, whichever occurs first. Objective response rate (ORR) defined as the proportion of patients who achieve complete response (CR) or partial response (PR), per RECIST 1.1 as defined by the

Investigator based on radiologic criteria. Assessments will be performed per timepoints as mentioned in the schedule of assessments (SoA) in the protocol.

Safety and tolerability of study treatment will be evaluated based on AE reports by the occurrence, nature, and severity of AEs as categorized by the Common Terminology Criteria for Adverse Events (CTCAE) v5.0. Timepoints will be performed as mentioned in the SoA.

[figure not shown]
Patients will receive study treatment until disease progression (PD), intolerable toxicity, or withdrawal from the study. Disease response/progression will be based on tumor assessments at timepoints specified in the SoA.

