**Table 1-1 Study Objectives and Endpoints**

Objectives	Endpoints
Primary 

To evaluate preliminary anti-tumor activity of selinexor with pembrolizumab versus standard of care (SOC)

	

Progression-free survival (PFS), as assessed by the investigator per RECIST1.1 assessed from randomization until disease progression or death from any cause, whichever occurs first

Secondary 

To evaluate preliminary anti-tumor activity of selinexor with pembrolizumab versus SOC

	

Overall survival (OS), defined as time to death due to any cause from the randomization date

ORR, defined as the proportion of patients who achieve complete response (CR) or partial response (PR), per RECIST 1.1 as defined by the Investigator based on radiologic criteria

DCR is defined as the proportion of patients who have best response of PR or better, or at least 12 continuous weeks of SD before disease progression or initiating a new antineoplastic treatment.

PFS at 6 months, OS percent in 6 months, OS percent in 12 months, DOR, and DCR per RECIST 1.1

[figure not shown]

• To evaluate preliminary anti-tumor activity of selinexor only versus SOC

	

• Overall survival (OS), defined as time to death due to any cause from the randomization date

• ORR, defined as the proportion of patients who achieve complete response (CR) or partial response (PR), per RECIST 1.1 as defined by the Investigator based on radiologic criteria

• PFS at 6 months, OS percent in 6 months, OS percent in 12 months, DOR, and DCR per RECIST 1.1

• Progression-free survival (PFS) per RECIST 1.1 assessed by the investigator from the randomization date

• To describe the safety and tolerability of selinexor with and without pembrolizumab

	

• Safety and tolerability of study treatment will be evaluated based on AE reports by the occurrence, nature, and severity of AEs as categorized by the Common Terminology Criteria for Adverse Events (CTCAE) v5.0

Exploratory
 
CCI
 	

CCI

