### 1.3. DETERMINATION OF SAMPLE SIZE

CCI

Given above assumptions, the total sample size is approximately 78 patients with 26 in each arm.

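### Randomization is stratified, but the Cox models for the PFS hazard ratios name no stratum; the unstratified HR is valid but marginal, and lies closer to 1 if the factor is prognostic

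*SAP*

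**What the plan says.** Section 1.1 of the SAP states that patients are "randomized to Arm A, B or C based on the following stratification factor". The factor's name and levels are redacted.

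Table 1-1 makes the primary objective comparative, selinexor plus pembrolizumab against standard of care, with investigator-assessed PFS as the endpoint. Section 1.3 gives the size: "the total sample size is approximately 78 patients with 26 in each arm". Section 4 says that "All efficacy analyses will be performed on the ITT Population".

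The between-arm model is in Section 4.2: "Cox proportional hazards regression models will be used to estimate a HR for the risk of progression". It is applied to each selinexor arm against control and also to "the selinexor and pembrolizumab arm versus selinexor only arm comparisons". No stratum or covariate is named, and the section carries no redaction mark. Section 4.1.3 adds only that "percentiles for PFS and associated 95% CIs will be estimated based on the KM method". Section 2.7 plans no subgroup analyses. No visible text carries the randomization factor into an analysis.

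**The concern.** The usual practice is to analyse by the factor used to randomize. Read literally, Section 4.2 does not, and its HR is the only between-arm PFS measure visible in the plan. Two things follow if the factor is prognostic:

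- **Target.** The HR is not collapsible. An unstratified model averages over patients with different baseline risk, and its HR lies closer to 1 than the HR within levels of the factor.
- **Precision statement.** Stratified randomization makes the estimate vary less between hypothetical repeats of the trial. The usual unstratified standard error does not know this, so under the null the interval is too wide.

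There is also a prespecification issue that does not depend on the factor's strength. Section 4.2 is silent and does not expressly exclude strata. Two analysts could therefore fit different models to 52 patients in an open-label trial with investigator-assessed PFS.

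**Working it through.** **Inputs from the SAP.** One stratification factor (Section 1.1); Cox model without strata (Section 4.2); 26 patients per arm, so 26 + 26 = 52 per pairwise comparison (Section 1.3). The plan states no figure on this point, and the sample-size assumptions are redacted, so there is nothing to reproduce first.

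**Assumed inputs.** True within-stratum treatment HR 0.50, or 1 for the null; exponential PFS with reference-level control median 2.5 months; uniform administrative censoring at 6 to 18 months; levels exactly balanced across arms; factor HR 1, 1.5, 2 or 3. There were 40,000 simulated trials per scenario and a mean of 45 to 51 events. Monte Carlo error is about 0.25 points for the rate at which the CI excludes 1, and 0.11 for null rejection and coverage.

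**Formulas.** With treatment indicator x and n1, n0 patients at risk in each arm at an event, p = e^b·n1 / (e^b·n1 + n0). The estimate b solves Σ(x − p) = 0, SE = 1/√Σp(1 − p), and the 95% CI is exp(b ± 1.96·SE). The stratified model is the same except that n1 and n0 are counted within the patient's own stratum.

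**Results, two equal levels (13/13 per arm), unstratified v stratified.** The HR is a geometric mean at true HR 0.50.

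| Factor HR | HR | Null rejection | CI excludes 1 | Same-trial HRs differ by >10% |
|---|---|---|---|---|
| 1 | 0.49 v 0.49 | 5.2% v 5.1% | 62.0% v 60.1% | 13% |
| 1.5 | 0.50 v 0.49 | 5.0% v 5.4% | 61.4% v 61.4% | 22% |
| 2 | 0.52 v 0.49 | 4.3% v 5.4% | 57.5% v 62.0% | 37% |
| 3 | 0.56 v 0.49 | 3.2% v 5.3% | 49.3% v 62.5% | 60% |

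No efficacy test is visible in the SAP, so the CI excluding 1 is only a yardstick. The two models disagree on it in 6%, 7%, 10% and 17% of trials.

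On the log scale the shift at factor HR 2 is ln(0.52/0.49) = 0.059. Against an unstratified SE of 0.304, that is 0.059/0.304 ≈ 0.2 standard errors.

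**Other layouts.** Change in the CI-excludes-1 rate from stratifying, in percentage points:

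| Layout per arm | Factor HR 1 | 1.5 | 2 | 3 |
|---|---|---|---|---|
| Two equal levels (13/13) | −1.9 | 0.0 | +4.5 | +13.2 |
| 80/20 (21/5) | −1.8 | −0.5 | +1.4 | +5.0 |
| Four levels, unpooled (7/7/6/6) | −4.5 | −3.9 | −1.9 | +3.2 |
| Four levels pooled to two (14/12) | −1.7 | −0.8 | +0.9 | +5.0 |

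**Second check, different assumptions.** This used a geometric-mean control median of 2 months, censoring at 6 to 12 months, permuted blocks of 2 within a two-level factor, and 4,000 trials per scenario. With equal levels the median unstratified HR was 0.52 and 0.56 at factor HR 2 and 3, against 0.50 stratified. Null rejection was 4.0% and 2.9%. With 25% of patients in one level the unstratified HRs were 0.515 and 0.536. With 500 per arm and equal levels they were 0.53 and 0.56, so the shift is a difference of target and not a small-sample artefact.

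**Why the interval is conservative under the null.** In this second check the unstratified estimate had an actual SD of 0.270 and a mean reported SE of 0.296 at factor HR 3. The implied rejection rate is 2·[1 − Φ(1.96 × 0.296/0.270)] = 2·[1 − Φ(2.149)] ≈ 3.2%, in line with the 2.9% counted. At factor HR 2 it is 2·[1 − Φ(1.96 × 0.293/0.281)] = 2·[1 − Φ(2.044)] ≈ 4.1%, against 4.0% counted.

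**The case against.** The case for leaving the model alone is substantial.

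- **Estimation is not worse without strata.** Section 4.2 uses the model to estimate an HR. In the first simulation, coverage of the within-stratum HR is 94.6–95.3% unstratified and 94.8–95.2% stratified. The RMSE of the log HR is lower unstratified in all 12 scenarios (for example 0.303 v 0.327 at factor HR 2, two equal levels). This stands.
- **The SAP never says that it wants the within-stratum HR.** A marginal HR is a legitimate target. This stands, but the plan does not choose it either.
- **The balance is not wasted.** It already protects the unstratified point estimate; only the SE fails to credit it. This stands.
- **The gain depends on redacted facts.** Of the 16 changes tabulated across layouts, stratifying helps in 7, makes no difference in 1 and hurts in 8. Neither the factor's strength nor its levels are visible. This limits the priority.
- **The factor may be dealt with elsewhere.** Sections 1.3 and 2 contain redactions, and the protocol is not at hand. That is possible, but Section 4.2 is where the SAP chooses the model, and its text is complete as shown.

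A reader might infer that the unstratified analysis is invalid or inflates false positives. It does not: null rejection was at or below about 5% throughout the two-equal-level results. A reader might also infer that the SAP departs from a stratified protocol model. Section 1.6 declares no modifications and the protocol is not shown, so the documents do not support that.

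**Conclusion.** The gap is real but limited. Randomization uses one factor and the Section 4.2 Cox models name no stratum. Followed literally, the plan yields a valid marginal HR. If the factor is prognostic, this HR lies closer to 1 than the within-stratum HR and its CI is conservative under the null.

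In the illustrated two-equal-level setting the attenuation is modest at factor HR 2, larger at 3 and negligible at 1.5 or below. It shrinks with uneven levels, and at factor HR 2 four unpooled levels reverse the gain in the CI-excludes-1 rate. These sizes rest on assumed inputs, because the factor is redacted; they are not this trial's known effect. The sponsor knows the factor and can place the trial within the range.

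The firmest reason to act is prespecification. Even with a non-prognostic factor, the two models give HRs more than 10% apart in 13% of simulated trials, so the choice should be written down. Priority is low to moderate.

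**What to change.** In Section 4.2, state that the PFS HR and its 95% CI come from a Cox model stratified by the randomization factor, using the value recorded at randomization, and that the unstratified HR is reported as a sensitivity analysis. If the factor has more than two levels or any sparse level, name the pooling in the SAP now, without looking at data by arm. Use the same strata for all three arm comparisons, and for OS if an OS HR is reported. If the sponsor prefers the marginal HR, Section 4.2 should say so and give the reason.

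The cost is two sentences and one programming statement. Under the assumed inputs, at factor HR 2 with two equal levels, the SE of the log HR rises from 0.304 to 0.316 (0.316/0.304 = 1.04, about 4%) and the RMSE from 0.303 to 0.327 (0.327/0.303 = 1.08, about 8%). If the factor is not prognostic, the chance that the CI excludes 1 falls by about 2 points with two levels, 4.5 with four unpooled levels, and 1.7 with four levels pooled to two.

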##### **3.2.2. Baseline Characteristics**

Summary statistics including the number and percentage of patients will be presented for the following variables:

- Baseline height (cm)/ weight (kg)/ body surface area (m^2)/ BMI (kg/m^2)
- Baseline ECOG performance status

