### **3.2.3. Prior Antineoplastic Therapy**

Prior antineoplastic therapy will be summarized with the following variables:

- Number of prior regimens of antineoplastic therapy
- Best response to prior regimens of antineoplastic therapy
- Days since discontinuation of most recent prior antineoplastic therapy the start of study treatment, which will be calculated as the date of first study treatment – stop date of most recent antineoplastic therapy+1
- Days since most recent disease progression to the start of study treatment

The detailed history of prior systemic therapy including start and end dates of the medication, best response, progression during or after therapy, as well as discontinuations due to, toxicity and/or intolerance may also be provided in a data listing.

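### Section 4.2 names no baseline covariate for the PFS Cox model, so as written it gives a valid but less efficient treatment-only hazard ratio with 26 patients per arm

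*SAP*

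**What the plan says.** PFS is the primary endpoint: "PFS is defined as the time from the randomization date until the date of first PD determined by PI per RECIST 1.1", or death. The between-arm model appears only in SAP Section 4.2: "Cox proportional hazards regression models will be used to estimate a HR for the risk of progression", for the comparisons "in the selinexor only or selinexor and pembrolizumab arm versus the SOC control arm, and the selinexor and pembrolizumab arm versus selinexor only arm comparisons". No covariate or stratum is named there, and the paragraph shows no redaction mark.

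Two candidate covariates are already collected. Section 3.2.2 lists "Baseline ECOG performance status" and Section 3.2.3 lists "Number of prior regimens of antineoplastic therapy". Both serve only descriptive summaries, and neither is called prognostic.

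Section 1.1 says that patients are "randomized to Arm A, B or C based on the following stratification factor"; the factor itself is redacted. Section 1.3 gives the size, "the total sample size is approximately 78 patients with 26 in each arm", with its assumptions redacted. The primary objective in Table 1-1 is "To evaluate preliminary anti-tumor activity of selinexor with pembrolizumab versus standard of care (SOC"). The visible text states no hypothesis test, alpha or power for PFS.

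**The concern.** Each pairwise comparison rests on 52 patients. At that size a factor outside the stratification can differ noticeably between arms by chance. A treatment-only Cox model makes no use of such a factor even when it is recorded for every patient. If the factor is prognostic, the treatment-only hazard ratio lies nearer 1 than the covariate-conditional one, and a real effect is less likely to show in the confidence interval. At stake is how clearly a small phase 2 trial reads its primary comparison.

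Silence about the model also leaves room to choose covariates after the data have been seen, in an open-label trial with investigator-assessed progression.

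**Working it through.** **Inputs from the SAP.** 26 patients per arm and 3 x 26 = 78 in total, which agrees with Section 1.3. The design calculation behind 78 cannot be reproduced, because its inputs are redacted.

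**Assumed inputs.** True hazard ratio 0.5 or 0.6; binary baseline factors at 50% prevalence; prognostic hazard ratios as shown below; exponential PFS; about 44 to 46 events among 52 patients; two-sided 5% Wald criterion, which is the same as asking whether the 95% CI excludes 1.

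**Step 1: chance imbalance.** For a 50% factor not used in stratification, the SD of the between-arm difference in proportions is sqrt(2 x 0.25 / 26) = 0.139, about 14 points. In simulation, differences of 20 points or more occurred in about 12 to 13% of trials. With 26 per arm that means at least 6 patients, since 5/26 = 19% and 6/26 = 23%.

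**Step 2: effect of a 1-SD imbalance.** With an assumed prognostic hazard ratio of 2.0, the log hazard ratio shifts by about 0.139 x ln 2 = 0.10, or about 10% on the hazard ratio. The standard error of the unadjusted log hazard ratio is about 0.32, so the shift is about a third of one standard error.

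**Step 3: chance that the 95% CI excludes 1, treatment-only versus adjusted.** The one-factor rows come from 4000 simulated trials per scenario, the two-factor rows from 3000 (simulation error about 2 points either way on each figure).

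| Assumed prognostic HR | True HR 0.5 | Gain | True HR 0.6 | Gain |
|---|---|---|---|---|
| One factor, 1.5 | 58.7% to 60.8% | 2.1 | 36.3% to 38.2% | 1.9 |
| One factor, 2.0 | 55.5% to 60.9% | 5.4 | 35.6% to 41.6% | 6.0 |
| One factor, 2.5 | 49.9% to 59.3% | 9.4 | 32.6% to 40.2% | 7.6 |
| Two factors, none prognostic | 59.5% to 58.1% | -1.4 | 37.8% to 38.2% | 0.4 |
| Two factors, 1.5 and 1.3 | 56.3% to 58.6% | 2.3 | 34.4% to 37.5% | 3.1 |
| Two factors, 2.0 and 1.5 | 51.4% to 58.4% | 7.0 | 31.3% to 37.0% | 5.7 |
| Two factors, 2.5 and 2.0 | 44.2% to 56.6% | 12.4 | 27.7% to 36.0% | 8.3 |

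**Step 4: where the gain comes from.** The interval does not become narrower. Take the two-factor case with prognostic hazard ratios 2.0 and 1.5 and a true hazard ratio of 0.5. The median unadjusted estimate is 0.53 with standard error 0.323, so |ln 0.53| / 0.323 = 1.97. The median adjusted estimate is 0.483 with standard error 0.340, so |ln 0.483| / 0.340 = 2.14. The estimate moves away from 1 by more than the standard error grows.

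**Step 5: validity.** With no treatment effect, two-sided type I error was 5.2 to 5.8% unadjusted and 5.4 to 5.7% adjusted with one factor. With two factors it was 4.2 to 5.8% and 5.4 to 6.4%. Both models are close to nominal. The two-factor Wald criterion is slightly liberal, which may account for part of the smallest gains in those rows.

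**The case against.** The strongest reply is that an unadjusted hazard ratio is a legitimate choice in a randomized, estimation-focused phase 2 trial. That stands, and several stronger readings that a reader might infer fail for related reasons.

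- **The SAP states that the model contains treatment only.** It does not. It is silent, and treatment-only is what results if the text is followed literally. The protocol, which is not at hand, may say more. Section 1.6 records no statistical modifications, so if the protocol does name covariates, Section 4.2 should carry them.
- **The unadjusted result is biased or invalid.** Step 5 shows otherwise: chance imbalance is already covered by the error rate. The movement toward 1 is non-collapsibility. The marginal and conditional hazard ratios are different estimands, and neither is an erroneous version of the other.
- **ECOG status and prior regimens are strong prognostic factors here.** The SAP does not say so. The size of the loss depends wholly on that assumption, and it is about nil if they have no effect.
- **The trial loses power against its design.** No efficacy test is visible and the design assumptions are redacted. The percentages describe a confidence interval excluding 1, not a planned test.
- **Both factors are left uncontrolled.** The redacted stratification factor could be one of them.

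A practical objection also stands. Section 2.2 does not impute missing baselines, while Section 4 requires ITT for all efficacy analyses. A complete-case adjusted model would drop patients, so the fix needs a missing-value rule.

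**Conclusion.** The point holds as a worthwhile improvement and does not identify an error that invalidates the analysis. As written, Section 4.2 leads to a treatment-only PFS hazard ratio and leaves recorded baseline information unused. At an assumed true hazard ratio of 0.5, one adjusting covariate with a prognostic hazard ratio of 1.5 to 2.5 raises the chance that the 95% CI excludes 1 by about 2 to 9 points. The figure of 12 points needs two strong, independent factors, both in the model. If the factors are not prognostic the difference is about nil, with a nominal loss of about 1 point that is within simulation error. These sizes rest on the assumed prevalence, prognostic effects, treatment effect and event count; none of these is in the visible text. The 14-point imbalance figure needs only the 26 per arm and a 50% factor outside the stratification.

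**What to change.** In Section 4.2, before database lock:

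- Specify a PFS Cox model with treatment plus baseline ECOG status (0 versus 1 or more), used in each of the three comparisons. If ECOG is the redacted stratification factor, use number of prior regimens instead, with its coding written out. Commit to one; do not leave the choice open.
- State how a missing covariate is handled so that all ITT patients stay in, for example by a missing category. Section 2.6 ties baseline to the first dose, so the rule should also cover patients randomized but never dosed, for example by taking the last value on or before randomization.
- Report the treatment-only hazard ratio beside the adjusted one, and say that the first is marginal and the second conditional on the covariate.

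The cost is a few sentences and one extra model per comparison, with no new data collection. The small downside is a conditional hazard ratio that must be read as such, with a slightly larger standard error.
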